## 6.3. Analyses of Primary Endpoints

### Safety:

The primary safety endpoint for this clinical study is a composite of major adverse events (MAE) defined as cardiovascular mortality, stroke, myocardial infarction, new need for renal replacement therapy, severe bleeding and re-intervention for study device related complications at 30 days. The safety endpoints on composite of major adverse events shall be analyzed via the Kaplan-Meier method.

In addition to the safety endpoint analysis, a summary of the percentage of patients who experience an early adverse event ( $\leq 30$  day post-procedure) will be reported for all adverse events. Additionally, linearized rates will be used to summarize adverse events for the late ( $> 30$  days) post-procedure period. The linearized rates will be reported as the number of events occurring after the early post-procedure period per year of patient survival.

### Performance:

The device success, procedural success and clinical success will be summarized by counts and percentages.

#### 6.4. Analyses of Secondary Endpoints

Mitral regurgitation reduction from baseline at 30 days, 6 months, 1 year and annually thereafter will be summarized with counts and percentages.

All-cause mortality rates at 30 days, 6 months, 1 year, and annually thereafter and corresponding 95% confidence intervals will be computed using the Kaplan-Meier algorithm with the standard errors being computed using Greenwood's formula.

Recurrent heart failure hospitalization at 30 days, 6 months, 1 year, and annually thereafter will be analyzed using Poisson regression.

Re-intervention rates for mitral regurgitation at 30 days, 6 months, 1 year and annually thereafter will be summarized with counts and percentages.

Composite of major adverse events (MAE) defined as cardiovascular mortality, stroke, myocardial infarction, new need for renal replacement therapy, severe bleeding and re-intervention for study device related complications at 6 months, 1 year and annually thereafter will be summarized with counts and percentages.

Change from baseline in Left Ventricular End Diastolic Volume (LVEDV), Left Ventricular End Systolic Volume (LVESV), Pulmonary Artery Systolic Pressure, 6MWT distance, BNP/NT-pro-BNP level, effective regurgitant orifice area (EROA) and mitral regurgitant volume at the protocol specified timepoints in the secondary endpoints and clinical outcomes section will be summarized by mean and standard deviation for the PP population. For the analyses of six minute walk test (6MWT), subjects unable to perform the walk due to a medical reason will be considered to have walked an actual distance of zero.

Change from baseline in Quality of Life (QoL) score, as measured by Kansas City Cardiomyopathy Questionnaire (KCCQ), and EQ5D at 30 days, 6 months and 1 year and annually thereafter will be

summarized by mean and standard deviation. Patients that are missing a baseline or follow up values will be excluded from the analysis.

Change from baseline in NYHA Functional Classification at 6 months, 1 year and annually thereafter will be presented as shift from baseline for each of the pre-specified follow-up periods. Subjects that are missing a baseline or follow-up values will be excluded from the paired analysis.

Change from baseline in tricuspid regurgitation at 6 months, 1 year and annually thereafter will be summarized with counts and percentages.

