### 2.2. Study Design

This is a multi-center (up to 20 sites), multi-national, prospective, single arm study. The analysis population will consist of 60 patients. No site will be allowed to enroll more than 20% of the analysis population. All enrolled study patients will be assessed for clinical follow-up at the following intervals: 30 days, 6 months, 1 year and annually for 5 years post implant procedure. In addition, the study allows for 0 to 3 roll-in patients per site where allowed, for a total maximum of 60 roll-in patients. The overall study therefore allows for up to 120 patients: 60 in the analysis population, and up to 60 additional roll-in patients.

Of the total enrollment, 45 patients will be enrolled in the U.S. at up to 9 clinical sites. In the event that the 60-patient analysis cohort fills prior to the completion of the US EFS cohort, the US EFS cohort may continue to enroll until completed.

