## 6. STATISTICAL ANALYSES

### 6.1. General Considerations

a. For continuous variables, summary statistics will include number of observations, mean, median, standard deviation, minimum, maximum, and 95% confidence intervals (based on normal distribution, unless otherwise specified) per table shells.

b. For categorical variables, summary statistics will include counts, percentages, and 95% Clopper-Pearson confidence intervals per table shells. In general, the denominator for the percentage calculation will be based on total number of subjects with evaluable data for a specified time point unless otherwise specified. Subjects with missing data will be excluded from the denominator.

c. Survival analysis techniques will be used to analyze the time-to-event variables. Summaries will include the number of subjects at risk, number of events, and number of subjects with the event. Subjects without events will be censored at their last known event-free time point. If this event-free time point occurs after the analysis time point, the days to event variable will be set equal to the analysis time point so that the subject will be included in the analysis. For subjects who did not have an event or early withdrawal and have not yet completed the analysis visit, they will be censored at their last information date. Time to first event curves will be constructed using Kaplan-Meier estimates and all post procedure results will be summarized with Kaplan-Meier estimates of event rates. Hazard ratios, confidence interval for the hazard ratios, and p-values may also be presented from a Cox proportional hazards model.

d. Descriptive statistics will be provided at each follow-up assessment, including change from baseline to subsequent time point for selected endpoints. Paired (i.e., subjects with available data at both baseline and respective time point) and unpaired data will be presented separately.

e. If insufficient data are available for summary statistics, then data will be provided only as listings.

f. Unless otherwise specified, descriptive analysis will be performed for all data. Nonparametric techniques may be used if the data does not meet the assumptions of parametric tests.

g. All analyses will be performed using SAS® Software version 9.4 or later (SAS Institute, Inc., Cary, NC).

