## 6.2. Handling of Missing Data

All statistical analyses on the functional endpoints will be performed using only those patients with available data required for endpoint analysis. No missing value imputation will be performed.

No imputation will be done if the date variables are completely missing. For partial dates, only adverse event (AE) onset date will be imputed as follows:

- 1) If both month and day are missing
  - a. If the AE onset year is the same year as index procedure then use index procedure date to impute this AE onset date
  - b. Otherwise, assign January 1st for this AE onset date
- 2) If only day is missing
  - a. If the AE onset year and month are the same as the procedure ones then use the index procedure date to impute the AE onset date
  - b. Otherwise, assign '01' as the day for the AE onset date

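### For the 6MWT, inability to walk scores 0 m while a patient who has died drops out, so death gives the better mean change; KCCQ/EQ-5D change and the NYHA shift are simply survivor-only

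*SAP*

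**What the plan says.** SAP 6.2 sets the general rule: "All statistical analyses on the functional endpoints will be performed using only those patients with available data required for endpoint analysis", and "No missing value imputation will be performed". SAP 6.1 applies the same principle to percentages: "Subjects with missing data will be excluded from the denominator".

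SAP 6.4 then treats the three functional measures differently.

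- **6MWT:** change is summarised by mean and standard deviation in the per-protocol population, with one special rule: "subjects unable to perform the walk due to a medical reason will be considered to have walked an actual distance of zero". SAP 3.2 places this endpoint at 6 months and 1 year only.
- **KCCQ and EQ-5D:** mean and standard deviation of change, with "Patients that are missing a baseline or follow up values will be excluded from the analysis". No score is assigned for illness or death.
- **NYHA:** change "will be presented as shift from baseline for each of the pre-specified follow-up periods", at 6 months, 1 year and annually. "Subjects that are missing a baseline or follow-up values will be excluded from the paired analysis". No mean is planned.

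Neither document says how a patient who died before a visit enters any of these summaries. Mortality is reported separately by Kaplan-Meier (SAP 6.4). A 1-year composite in SAP 6.6, FDA Individual Patient Success, requires the patient to be alive and improved.

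**The concern.** The zero-distance rule recognises that a patient too ill to walk has a bad outcome, which should count against the mean. Death before the visit is a worse outcome. Under the available-data rule it leaves no value, and the patient leaves the calculation. Within the 6MWT endpoint the ranking is therefore reversed: a patient too ill to walk lowers the mean by a share of the whole baseline distance, and a patient who dies does not lower it at all.

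KCCQ/EQ-5D and NYHA have no such reversal, because nothing is scored as worst. Their summaries still describe only survivors with data. For NYHA, which is tabulated annually to 5 years, the group described shrinks as deaths accumulate.

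With a single arm, no control group would reveal a change produced by selection. The study also aims to guide the design of later studies (SAP 2.1), so a 6MWT or KCCQ change that is too favourable could be carried forward as a planning value.

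**Working it through.** The documents give no expected change, standard deviation or power for these endpoints, so there is no planned figure to reproduce. The check is direct arithmetic on the consequence of the rule.

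**Inputs from the documents**
- n = 60: "The analysis population will consist of 60 patients" (SAP 2.2).
- Mortality: 5% a year for symptomatic severe MR (Protocol 3.3), and 6% at 1 year in the cited randomised clip trial (Protocol 3.4.3.3). 60 × 0.05 = 3 and 60 × 0.06 = 3.6, taken as k = 3 and k = 4 deaths by 1 year.
- Baseline 6MWT: 150 to 400 m is an entry criterion for functional MR only (Protocol 7.7.1).

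**Assumptions**
- Baseline B = 275 m, the midpoint of that range, also used for degenerative MR.
- Mean gain g = +30 m in the remaining patients; range 0 to 30 m.
- Every survivor has paired data.

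**6MWT formulas**
- The k patients die and are dropped: mean change = g.
- The same k are alive but score 0 m: mean change = [(n − k)g − kB]/n.
- Gap = k(g + B)/n.

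**6MWT results at 1 year**

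| k | Dropped | Scored 0 m | Gap |
|---|---|---|---|
| 3 | +30 m | (57 × 30 − 3 × 275)/60 = +14.8 m | 3 × 305/60 = 15.2 m |
| 4 | +30 m | (56 × 30 − 4 × 275)/60 = +9.7 m | 4 × 305/60 = 20.3 m |

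Each such patient moves the mean by 305/60 = 5.1 m. The smallest gap in the range is 3 × (0 + 150)/60 = 7.5 m; the largest is 4 × (30 + 400)/60 = 28.7 m. For scale, SAP 6.6 uses a gain of more than 25 m as its example of functional improvement.

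**KCCQ.** Assume baseline 50 and survivor change +15. If deaths were scored 0, +15 would become (57 × 15 − 3 × 50)/60 = +11.8 for k = 3, or (56 × 15 − 4 × 50)/60 = +10.7 for k = 4. This shows the size of survivor selection only; the SAP has no zero rule for KCCQ.

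**NYHA.** Assume 80% of survivors are in class I or II. Over all 60 patients that is 0.80 × 57/60 = 76.0% for k = 3, or 0.80 × 56/60 = 74.7% for k = 4. With the 20.8% 5-year mortality cited for the clip arm (Protocol 3.4.3.3), it is 0.80 × 0.792 = 63.4%.

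**The case against.** **Death may not be dropped at all.** The SAP never says that deaths are excluded. That is inferred from its silence together with the no-imputation rule, and a medical reason for not walking could be read to include death. This stands as a limit on the wording. It does not remove the problem: two programmers could read the rule differently and, on the figures above, produce 1-year means 15 to 20 m apart.

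**The two rules can be defended together.** A living patient who cannot walk has a functional status; a dead patient has none. Describing function while alive and reporting death separately is a recognised choice. If that is the intention, it should be stated and the tables labelled accordingly.

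**Safeguards exist.** Mortality is reported by Kaplan-Meier. SAP 6.1 gives the number of observations and presents paired and unpaired data separately. The FDA composite counts death as failure. The table shells are in a separate document (SAP 10) and may already contain a row for deaths. These points lower the weight of the concern. However, the mortality estimate is not tied to the functional summaries, paired and unpaired follow-up values both come from survivors, and the composite is a single 1-year measure with many other components.

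**Stronger readings a reader might infer.**
- That the reversal affects all three measures. It does not: the zero rule covers 6MWT only, and NYHA has no mean for a death to improve.
- That 6MWT looks better year after year as patients die. The endpoint stops at 1 year. The questionnaires are also scheduled only to 1 year (Protocol Table 1 and 7.8.7.8), although SAP 3.2 lists KCCQ and EQ-5D annually.
- That a true decline would be reported as a gain. This needs more deaths than the background rates suggest: at B = 275 m and g = +30 m, the zero-scored mean turns negative only at about 6 deaths, (54 × 30 − 6 × 275)/60 = −0.5 m.
- That the gap is a bias against what would have happened without the deaths. It compares two scoring rules. Had the same 3 or 4 patients lived and walked their baseline distance, the mean would be 57 × 30/60 = +28.5 m or 56 × 30/60 = +28.0 m.

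**Conclusion.** The point holds in a limited form. For 6MWT, the natural reading of SAP 6.2 with SAP 6.4 gives a better mean change when a patient dies than when the patient is alive but medically unable to walk. At the protocol's background mortality the difference is about 15 to 20 m at 1 year under the central assumptions, and 7.5 to 28.7 m over the range examined. For KCCQ/EQ-5D and NYHA the issue is ordinary survivor-only selection, which for NYHA grows over annual follow-up.

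The direction for 6MWT follows from the rules, given any death of a patient with a baseline walk and a positive g + B. The size rests on the assumed baseline and gain, on 3 to 4 deaths, and on complete data in survivors.

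The consequence is modest. These are descriptive secondary endpoints, no hypothesis test or success criterion depends on them, and the primary 30-day endpoints are unaffected. It is a worthwhile improvement to the reporting and not a flaw that threatens the study's conclusions.

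**What to change.** Keep the paired summaries and make these additions to SAP 6.4 and the table shells:

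1. State for each functional endpoint how a death before the visit is handled, and whether the 6MWT zero rule includes it.
2. Label the paired summaries 'among survivors with data' and show the number of deaths beside each paired n, separately from withdrawals and missed visits.
3. Add a 'died' category to each NYHA shift table.
4. For 6MWT (6 months and 1 year) and KCCQ, add a supportive proportion of all treated patients who are alive and improved, with death counted as not improved. Fix the improvement threshold in advance; SAP 6.6 already offers example values (more than 25 m, more than 10 points). State how living patients without data are counted.
5. For 6MWT, add a sensitivity analysis that scores death no better than inability to walk, that is, 0 m.

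No new data are needed, since dates of death are already required for the mortality analysis. The cost is one extra row or table per visit, and functional figures that look slightly less favourable.

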#### 6.5. Poolability Analyses

Poolability will be assessed for the primary safety endpoint. The percentage of patients with MAE will be summarized separately for patients from North America (including sites in US and Canada) and the rest of the regions. The fisher's exact test will be applied to assess the poolability of data from these two regions. If p-value is great than 0.05 based on the fisher's exact test, then MAE data from North America and the rest of the regions are deemed poolable and the percentage of patients with MAE for all patients will be summarized. If data are not poolable, then data will be explored to identify differences between these two regions.

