7 CLINICAL INVESTIGATION

7.1 Study Design

This is a multi-center (up to 20 sites initially), multi-national, prospective, single arm study. The analysis population will consist of 60 patients. No site will be allowed to enroll more than 20% of the analysis population in the primary cohort. All enrolled study patients will be assessed for clinical follow-up at the following intervals: 30 days, 6 months, 1 year and annually for 5 years post implant procedure. In addition, the study allows for 0 to 3 roll-in patients per site where allowed, for a total maximum of 60 roll-in patients. The overall study therefore allows for up to 120 patients: 60 in the analysis population, and up to 60 additional roll-in patients.

Following completion of the primary cohort of 60 patients in the analysis population (up to 45 of which may be US patients), an additional 50 patients will be enrolled in the U.S. at up to 15 clinical sites.

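### SAP 6.5 treats a non-significant Fisher test as showing that regional MAE data can be pooled, but with about 60 patients the test detects only very large regional differences

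*SAP*

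**What the plan says.** SAP 6.5 opens: "Poolability will be assessed for the primary safety endpoint". MAE percentages are first summarized separately for "North America (including sites in US and Canada) and the rest of the regions", and Fisher's exact test is then applied. The decision rule begins: "If p-value is great than 0.05 based on the fisher's exact test, then MAE data from North America and the rest of the regions". When that condition holds, the plan's conclusion is that the two sets of data "are deemed poolable and the percentage of patients with MAE for all patients will be summarized". The other branch reads: "If data are not poolable, then data will be explored to identify differences between these two regions".

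On size, SAP 2.2 states: "The analysis population will consist of 60 patients". It adds: "Of the total enrollment, 45 patients will be enrolled in the U.S. at up to 9 clinical sites". Protocol 7.1 treats 45 as a ceiling: "Following completion of the primary cohort of 60 patients in the analysis population (up to 45 of which may be US patients").

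Neither document gives an expected MAE rate, a margin for an acceptable regional difference, an interval for that difference, or the power of the test. Protocol section 9 contains no poolability test, so SAP 6.5 is the only place where the rule appears.

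**The concern.** Failing to reject equality is not evidence of equality. It supports similarity only if the test would probably have rejected when the regions differed by an amount that matters. With about 60 patients, perhaps 15 of them in the smaller region, and a binary endpoint that may be uncommon, that condition is doubtful.

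At stake is a statement about the primary safety endpoint. A reader told that the regions were tested and found poolable would take it as reassurance that device safety is similar across regions. One stated study objective is to guide future study designs, so that reassurance could be carried forward.

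**Working it through.** **Inputs from the documents.** Fisher's exact test, threshold 0.05 (SAP 6.5); 60 patients (SAP 2.2); 45 US patients (SAP 2.2) or up to 45 (Protocol 7.1).

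**Assumptions.**
- The test is two-sided; the SAP does not say.
- MAE is 5% in one region and 10%, 15%, 20% or 30% in the other.
- The split is 45/15, 40/20 or 30/30 (North America/rest). The real split is open: 45 is a ceiling in the protocol; the SAP counts its 45 within total enrollment, which can include roll-ins; North America includes Canada; and the primary population is per-protocol, so it may be smaller than 60.

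The plan states no power, so there is no figure of its own to reproduce.

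**Step 1. Chance that the rule declares the regions not poolable.** With a and b events among n₁ and n₂ patients,

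Power = Σₐ Σ_b Bin(a; n₁, p₁) · Bin(b; n₂, p₂) · 1[Fisher p(a, b) ≤ 0.05],

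summed exactly over all outcomes.

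| Split (NA/rest) | Region with the higher rate | 5% v 10% | 5% v 15% | 5% v 20% | 5% v 30% |
|---|---|---|---|---|---|
| 45/15 | rest | 8.1% | 20.2% | 35.3% | 65.6% |
| 45/15 | North America | 0.3% | 1.5% | 9.0% | 47.9% |
| 40/20 | rest | 9.2% | 23.4% | 40.9% | 73.0% |
| 40/20 | North America | 1.8% | 9.9% | 26.4% | 64.0% |
| 30/30 | either | 1.9% | 9.3% | 24.1% | 63.1% |

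With no true difference (5% in both regions) at 45/15, the rejection rate is 1.4%, so the test runs well below its nominal 5%. At 45/15 with 5% in North America, 80% power needs about 37% in the rest. At the first analysis of 30 patients (SAP section 4), with an assumed 20/10 split and the higher rate in the rest, power for 5% versus 10-20% is 3-17%.

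**Step 2. What the rule would do with particular results at 45/15.** These need no assumed true rate, only the split.

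Take 2/45 versus 3/15, five events in all. The hypergeometric probability of k events in the smaller group is C(15,k)·C(45,5−k)/C(60,5), with C(60,5) = 5,461,512.
- k = 3: 455 × 990 / 5,461,512 = 0.0825
- k = 4: 1,365 × 45 / 5,461,512 = 0.0112
- k = 5: 3,003 / 5,461,512 = 0.0005
- k = 0 has probability 0.224, above 0.0825, so the opposite tail adds nothing.

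The sum before rounding is p = 0.094.

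| North America | Rest | Fisher p | Newcombe 95% CI, rest minus NA (points) | Under the rule |
|---|---|---|---|---|
| 2/45 (4.4%) | 3/15 (20.0%) | 0.094 | −1.0 to +40.9 | poolable |
| 3/45 (6.7%) | 4/15 (26.7%) | 0.058 | +0.7 to +45.7 | poolable |
| 11/45 (24.4%) | 0/15 (0%) | 0.0505 | −38.7 to −1.6 | poolable |

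The Newcombe limits come from the Wilson limits of each proportion. For the first row these are 1.2-14.8% and 7.0-45.2%, and the difference is 15.6 points. Lower limit: 15.6 − √[(20.0 − 7.0)² + (14.8 − 4.4)²] ≈ −1.0. Upper limit: 15.6 + √[(45.2 − 20.0)² + (4.4 − 1.2)²] ≈ +40.9.

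With 2/45 in North America, the rest needs 4/15 (26.7%) before p falls to 0.05 or below. With 0/15 in the rest, North America needs 12/45 (26.7%).

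**The case against.** The strongest defence is that little hangs on the rule, and most of it stands.
- SAP 6.5 reports MAE by region before the test and whatever its result. In the first example a reader would see 4.4% and 20.0% side by side.
- SAP 6.3 analyses the primary safety composite by Kaplan-Meier and does not make this conditional on 6.5. A reader might infer that the primary safety result depends on the test; the documents do not support that.
- The study is single-arm and descriptive (Protocol 9.3, SAP 6.1), with no performance goal or hypothesis for MAE, so no confirmatory conclusion turns on the label.
- SAP 6.1 provides Clopper-Pearson intervals for categorical variables according to table shells. Those are in a separate document not seen here, so regional intervals may already be planned.

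A reader might also conclude that pooling is virtually automatic. That fits equal or nearly equal rates, but not every scenario: at 45/15 with 5% in North America and 20% elsewhere the rule declines to pool 35% of the time, and at 5% versus 30% it declines in 48-73% of cases across the splits shown.

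Finally, no method gives about 60 patients useful regional precision, and an interval without a prespecified margin cannot itself justify a claim of poolability. That is right, and it is a reason to make no such claim.

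What the defence does not meet is the inference itself: a p-value above 0.05 is still turned into a positive statement that the data are poolable.

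**Conclusion.** The point holds in limited form. At this sample size p > 0.05 does not support calling the regional MAE data poolable. For 5% versus 10-20%, the chance of detecting the difference runs from 0.3% to 41% across the three splits and both directions. These figures rest on assumed rates, assumed splits and a two-sided test; they are not properties stated in the plan. The observed-result examples rest only on the 45/15 split.

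The consequence is confined to the label and the crude all-patient percentage. Read literally, SAP 6.5 ties that percentage to the passing branch, so it is also unclear whether it would be reported when p ≤ 0.05. The documents do not support the stronger readings that the primary Kaplan-Meier result is compromised or that pooling is assured whatever the data show. This is a SAP correction worth making, not a threat to the study's main analysis.

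**What to change.** In SAP 6.5:
- Delete the p > 0.05 decision sentence and the conclusion that the data are poolable.
- Report MAE by region and overall unconditionally, each with the Clopper-Pearson 95% interval already named in SAP 6.1.
- Add the between-region difference with a Newcombe 95% interval. Name that one method in advance, because interval and test can disagree: for 3/45 versus 4/15 the Newcombe interval excludes zero while Fisher's p is 0.058.
- Keep Fisher's p-value, if wanted, as descriptive only, and state whether it is two-sided.
- State that the data cannot exclude regional differences within the interval.

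The cost is one SAP edit and one extra interval, with no new data or patients. The sponsor loses an automatic statement that the regions are poolable, and the interval will be wide: about 42 points in the 2/45 versus 3/15 example (−1.0 to +40.9). That width is a fair picture of what the data can say about regional differences.
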